
Rationale for selected dose range in the present project: Here, 224 subjects high in PSI will be randomized to a single oral dose of PREG 400mg (n=112), or placebo (PBO, n=112) to ascertain dose of administration. The rationale for the selected dose range is the following: First, clinical trials showed that PREG 25–500 mg/day is safe and well tolerated in humans. Second, Sripada and colleagues made the compelling basic science discovery that a single dose (400mg) of PREG up-regulates ALLO in young adults (See Fig. 1) and reduces activation of brain areas underlying negative emotions processing.

Steroid (pg/ml)	Placebo (n=15)		Pregnenolone Group (n=16)			
	Baseline (Mean ± SD)	Endpoint (Mean ± SD)	Baseline (Mean ± SD)	Endpoint (Mean ± SD)	ï	р
Pregnenolone	1378.8 ± 579.1	1190.8 ± 468.5	1238.0 ± 378.7	3943.6 ± 696.3	12.3	<.001
Allopregnanolone	114.3 ± 49.6	118.1 ± 76.5	112.3 ± 40.9	802.2 ± 280.7	10.2	<.001
Pregnanolone	470.6 ± 200.8	490.5 ± 135.6	352.0 ± 106.6	517.4 ± 96.2	3.2	.004

Fig. 1. Steroid and metabolite levels in Sripada et al.'s 2013. *T-tests were conducted on change scores (steroid levels at endpoint minus steroid levels at baseline). Pregnenolone group received an acute, oral dose of PREG 400mg.

Based on pharmacokinetic data in humans, we expect the peak serum concentration of ALLO to occur approximately 2 hours after acute, oral administration of PREG 400mg. Saliva levels will be measured at the following 3 time points: -0.5, 2.0, 3.0 to provide various measures and correlations with behavioral tasks and correlations with serum levels.

4. Aims & Hypotheses:

Specific Aim 1: Assess PREG on levels of ALLO in a dose-finding design. Relative to PBO, PREG will dose-dependently increase and normalize ALLO levels in individuals high in PSI such that it will be comparable to Matched Healthy Controls (MHC) (Hypothesis 1A).

Specific Aim 2: Examine PREG on attentional bias to social threats and depressive symptomatology in individuals who are high in PSI. Relative to PBO, PREG will reduce depressive symptomatology and attentional bias to social threats and improve intention understanding and perception of others in individuals high in PSI (Hypothesis 2A). Hypothesis 2B: In PSI and MHC, depressive symptomatology and attention to social threats will correlate negatively with ALLO levels.

5. Duration of the study: The total duration of the entire study on campus is between 4 and 4 $\frac{1}{2}$ hours maximum.

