7. RESEARCH METHODS

The Approach

This project will comprise a randomized, placebo- controlled, between-subjects design, where we will couple a validated behavioral paradigm on attention to social threats with an acute pharmacological challenge with oral pregnenolone (PREG) or placebo (PBO) in subjects high in PSI and test behavioral responses and neuro-active steroid levels *prior and after study oral drug administration*. In the present project, 224 PSI subjects will be randomized to a single oral dose of PREG 400mg (n=112), or placebo (PBO, n=112) to ascertain dose of administration. In this project, participants will attend a single laboratory visit. During this single session, behavioral responses and subjective feelings will be tested at two time points (once before and once after). Neuro-active steroids will be measured from blood and saliva at several points to ascertain they correlate. A group of Matched Healthy Controls (MHC) who are low in PSI (n=12) and will not receive PREG but will otherwise complete all questionnaires of the study. Participants will be recruited from the University of Chicago and in the community.

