All participants must be 1) Male; 2) Aged 21-80 (inclusive); 3) High in PSI (PSI > 42, except for controls who should have a score < 42); 4) Do not meet Mini-International Neuropsychiatric Interview (M.I.N.I) criteria for psychiatric illness (except untreated major depressive disorder); and 5) BMI <30 (as ALLO levels are higher in obese than non-obese individuals). Key Exclusion Criteria: Female, as ALLO levels vary as a function of the menstrual cycle; 2) Aged < 21 or > 80; 3) Low in PSI (PSI < 42, except for controls)); 4) meet M.I.N. I criteria for psychiatric illness, besides untreated major depressive disorder; 5) Uncorrected vision; 6) Medical history of cancer; 7) Medical history of condition that might be made worse by exposure to estrogen or testosterone; 8) Recent steroid use; 9) Currently taking psychotropic medication; 10) History of seizures, neurological disorders; 11) History of TBI with loss of consciousness and/or with current cognitive impairment related to TBI; 12) Under hormonal therapy (including, but not limited to, testosterone); 13) Any unstable medical illnesses; 14) Lifetime history of bipolar disorder, schizophrenia, or psychotic disorder; 15) Current or recent (past 3 months) substance abuse or dependence; 16) Currently taking any medications that have/may have unfavorable interactions with Pregnenolone; 17) History of irregularities of heart rhythm, or heart palpitations; 18) obesity (defined as BMI>30); 19) illegal drug use as determined by urine drug screen.

Rationale: The recruitment and random assignment of young adults high in PSI to the PREG and PBO conditions allow us to ascertain the effects of PREG on PSI, depressive symptoms, and attentional biases for social threats. In addition, the recruitment of participants between the ages of 21 and 80 years will allow us to compare emotional and neurobiological findings across groups without the confounder of age effects.

Upon receipt of written consent, subjects will fill out self-report questionnaires and undertake practice on our behavioral paradigm.

During the visit, the following will occur:

- The subject will complete several questionnaires, including questions about perceived social isolation and questions about his mood.
- The subject will do a visual task on a computer.
- If the subject has low perceived isolation, the study drug will NOT be given.
- The subject will be asked to provide blood samples throughout the visit so that we

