can see how his blood hormones change at different times. The experimenter will draw blood from the subject's arm three times: 1) 30 minutes after your arrival at the high-performance electrical neuroimaging laboratory, 2) one 2 and 30mn later and 3) again an hour later. About 1 teaspoon of blood will be taken each time.

- The subject will also be asked to provide saliva samples during the study at the same three times: 1) 30 mn after your arrival at the high-performance electrical neuroimaging laboratory, 2) one 2 and 30mn later and 3) again one an hour later. About 1 teaspoon of saliva will be taken each time. We ask the subject to provide saliva samples so that we can see how the samples are related to behavioral tasks and how the subject is feeling at different times in the study.
- The subject will watch a 2-hour-long relaxing movie in a quiet and relaxing environment.

Two hours after the subject takes the pill (drug or placebo), the following will occur:

- The subject will do the exact same behavioral visual task on a computer . Control subjects will perform the same tasks at the same time, except they will not take any pills.
- The subject will complete the same questionnaires again.
- The subject will wait for 30 minutes in a relaxing and quiet environment.
- The subject will be given a parking voucher or \$5 for public transportation and a \$60 monetary compensation for participating in the study.

Estimated Duration of Visit: Between 4 Hours and 4 ½ hours

In the event suicidal ideation or similar events take place during the study, the subject will be removed from the study and referred to the appropriate clinical resources.

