C.2.6. Neurosteroid Analyses: To compare ALLO results with Sripada et al.'s 2013, basal serum levels will also be taken (once prior to drug administration and once two hours after oral administration of the drug study) and analyzed using a gold-standard in the literature: a gas-chromatographic mass-spectrometric (GC-MS) approach. Serum levels of pregnenolone, progesterone, 5alpha-DHP and ALLO and pregnanolone (ALLO's steroisomer and GABA-active) will be measured. As in Majewaska et al (2014), saliva samples will be analyzed using the same gold standard GC-MS approach in ALLO literature i.e., a method that allow for accurate measurement in the femtomolar range of specific neurosteroids. We will ensure that participants will refrain from smoking, eating, drinking alcoholic, caffeinated, or juicy beverages, and brushing teeth at least one hour before the first saliva sample and between saliva samples.

C.2.7. General Statistical approach:

Demographic and self-report psychological measures: Statistical analyses for demographic and self-report measures will be computed using SPSS software. Prior to inferential analyses, descriptive statistics, including distributions, means, standard deviations, skewness, and kurtosis will be generated. Data will also be examined for the pattern and mechanism of missing data. Continuous data will be tested for normality and homogeneity of variance. Potential differences between the study groups in terms of demographic and behavioral measures will be explored using multivariate analysis of variance (MANOVA) or appropriate non-parametric tests as appropriate. The overall significance level for these analyses will be at 5% using two-tailed tests and effect sizes and confidence intervals will be reported. In addition, scores at self-report questionnaires will be analyzed via a 2 (Drug Type: PREG 400mg, or PBO) x 2 (time: before, after) repeated measures ANOVA to assess for main effects and interaction effects.

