Behavioral paradigms: Statistical analyses will be computed using SPSS software. Reaction times and performance data will be screened and any outliers will be removed based on each participant's trial-by-trial data. A trial will be removed if it differed by 3 standard deviations above or below the participant's mean. Prior to inferential analyses, descriptive statistics, including distributions, means, standard deviations, skewness, and kurtosis will be generated. Data will also be examined for the pattern and mechanism of missing data.

• For the *body language* paradigm: A 2 (Drug Type: PREG 400mg, or PBO) x 2 (type of stimuli: social, non-social) x 2 (nature of the stimuli: threat, non-threat) repeatedmeasures ANOVA will be performed on the reaction times and valence ratings to assess for main effects and interaction effects. P values, confidence interval, and effect sizes will be reported.

C.2.6. Power Analysis: Using G* power calculation software (Version 3.1.9.2; © Franz Faul, Edgar Erdfelder, Albert-Georg Lang, and Axel Buchner, 2006, 2009) for a within-between interaction in a repeated measures ANOVA, a total sample size of 36 for three groups will yield 95% power to detect a significant difference, with alpha = 0.05 and an effect size Cohen's *d of* 0.35 in the present project.

Note: The hormone tested in saliva and blood have the same origin from adrenals glands and gonads. Here we want to establish a correlation within the same subjects among the levels of the same neuro-active steroid determined in the blood and the saliva. We expect the hormone levels measured in saliva and in blood to be different in amount but to correlate.

Saliva samples will be analyzed using the same gold standard GC-MS approach in ALLO literature i.e., a method that allow for accurate measurement in the femtomolar range of specific neurosteroids. We will ensure that participants will refrain from smoking, eating, drinking alcoholic, caffeinated, or juicy beverages, and brushing teeth before each saliva sample.

7. Special Precautions:

Pregnenolone side effects, danger, risk, and the harm it can cause

Overstimulation and insomnia -

Irritability, anger or anxiety -

Acne can occur due to the probable conversion of this hormone into androgens

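### The body-language ANOVA names no session and gives the pre-dose score no defined role as a baseline, although the task is run both before and after dosing

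*Combined protocol and SAP*

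**What the plan says.** Section 4 (Aims & Hypotheses) states Hypothesis 2A: "Relative to PBO, PREG will reduce depressive symptomatology and attentional bias to social threats". Section 7 (The Approach) says that "behavioral responses and subjective feelings will be tested at two time points (once before and once after" the drug or placebo. The visit list puts the task early in the visit ("The subject will do a visual task on a computer") and again two hours after the pill ("The subject will do the exact same behavioral visual task on a computer").

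C.2.7 then gives two models.

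- Self-report scores get a "2 (Drug Type: PREG 400mg, or PBO) x 2 (time: before, after) repeated measures ANOVA".
- The body-language task gets "A 2 (Drug Type: PREG 400mg, or PBO) x 2 (type of stimuli: social, non-social) x 2 (nature of the stimuli: threat, non-threat", as a repeated-measures ANOVA that "will be performed on the reaction times and valence ratings", examining main effects and interactions.

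The second model contains no time factor, change score or baseline covariate, and names no session. The only other analysis that touches these data is general: group differences in "demographic and behavioral measures will be explored using multivariate analysis of variance (MANOVA") or non-parametric tests. It is exploratory and names no session either.

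**The concern.** The authors wrote time into the self-report model and left it out of the body-language model a few lines later. A reader cannot tell whether this means that only post-dose data are analysed, or that a time factor was dropped by oversight. Pooling both sessions is a third way to run the same ANOVA, less likely but not ruled out.

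These are different tests with different precision. Because this is the only model specified for the attentional-bias part of Hypothesis 2A, the choice among them could be made after the data are seen. The model also examines all main effects and interactions without saying which one tests the hypothesis. Meanwhile a baseline that every randomised participant provides has no stated use in the efficacy test.

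**Working it through.** **Does the power paragraph settle the matter?** It claims 95% power with 36 subjects in three groups for a within-between interaction, alpha 0.05, effect size 0.35. The noncentrality is f² × N × m / (1 − rho). Taking 0.35 as Cohen's f, m = 2 measurements and rho = 0.5 (m and rho are assumptions): 0.1225 × 36 × 2 / 0.5 = 17.64, with 2 and 33 degrees of freedom, giving 95.7%. The figure reproduces. Read literally as d = 0.35 (f = 0.175), power is 41.8%. Two measurements fit a pre/post design, but the paragraph does not say what enters the body-language model.

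**Inputs for the comparison**

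- 112 per arm, from section 7. Also 12 per arm, because section 9 and the power paragraph give a total of 36; this assumes three equal groups.
- Score per participant and session: (social threat minus social non-threat) minus (non-social threat minus non-social non-threat). The arm difference in this score is the planned Drug × type × nature interaction.
- rho, the pre/post correlation of the score: not in the documents, so 0.2, 0.5 and 0.7 are shown. Low values are plausible. C.2.2 gives 2 blocks × 28 = 56 pictures per session, or 14 per cell if split evenly over four cells (assumption), and a difference of differences on 14 trials per cell is noisy.
- Equal variance in the two sessions (assumption).

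**Baseline-adjusted against post-dose only.** With n per arm, and including the cost of estimating the slope, the variance ratio is (1 − rho²) × (1 + 1/(2n − 4)).

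| rho | n = 112: factor 1 + 1/220 | n = 12: factor 1 + 1/20 |
|---|---|---|
| 0 | 1.0045 | 1.0500 |
| 0.2 | 0.96 × 1.0045 = 0.964 | 0.96 × 1.05 = 1.008 |
| 0.5 | 0.75 × 1.0045 = 0.753 | 0.75 × 1.05 = 0.788 |
| 0.7 | 0.51 × 1.0045 = 0.512 | 0.51 × 1.05 = 0.536 |

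The ratio equals 1 at rho = 1/√(2n − 3): 1/√221 = 0.07 and 1/√21 = 0.22. The worst cost, at rho = 0, is 0.4% and 5% extra variance.

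**Drug × Time (change score) against post-dose only.** The ratio is 2(1 − rho): 1.6, 1.0 and 0.6. Copying the self-report structure loses precision when rho is below 0.5.

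**Both sessions pooled without a time factor.** The expected pre-dose drug difference is zero, so the expected contrast is (0 + δ)/2 = δ/2. The variance of the mean is (1 + rho)/2 of the single-session variance. The standardised effect is multiplied by 0.5/√((1 + rho)/2), which at rho 0.5 is 0.5/0.866 = 0.58.

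**Illustrative power only.** Assume a post-dose difference of 0.35 SD, 112 per arm, two-sided 5%, rho 0.5: post-dose only 74%, adjusted 85%, pooled about 33%. At 12 per arm, post-dose only gives 13% and adjusted 15%. If 0.35 is instead f for a 2 × 2 within-between interaction, the noncentrality is 0.1225 × 224 × 2 / 0.5 = 109.8, the same as a 1.4 SD difference (1.4² × 112 / 2 = 109.8), and every option exceeds 99% at 112 per arm.

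**The case against.** C.2.7 does give the factors, both outcomes, the trial-level outlier rule and the reporting. A reader might infer that the test is wholly unspecified; it is not. What is missing is narrower: the session, the role of baseline, and the target effect.

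A reader might also infer that the baseline will definitely be discarded. The text does not say so. Section 7 describes testing before and after dosing, and the power paragraph reproduces with two measurements, so an omitted time factor is a fair reading, and that would use the pre-dose data. The MANOVA might also be a comparability check on pre-dose data, though that would give baseline no place in the efficacy test.

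The power figures deserve little weight. They rest on an assumed effect and an unknown rho, the largest loss comes from a pooling that the documents nowhere propose, and under the f reading the choice hardly affects power at 112 per arm. The variance ratios and the halving do not depend on the effect size and are unaffected.

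Finally, covariate adjustment is one sound choice among several, and at 12 per arm with rho near 0.2 it gains nothing. That limits the benefit. It does not remove the need to state which session is analysed and how baseline enters. Which of the two outcomes is the main one is a separate question and is not argued here.

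**Conclusion.** The gap is real and limited. The task is run in two sessions, and the single efficacy model given for it neither names a session nor gives the pre-dose score a role as baseline. The documents do not support a charge of bias: post-dose only is a valid randomised comparison. Nor do they support a statement that sessions will be pooled or that power will fall to a particular value.

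What can be said is that adjusting for the score already collected cuts variance by about 4%, 25% and 49% at rho 0.2, 0.5 and 0.7 with 112 per arm. With 12 per arm it changes variance by +1%, −21% and −46%. The most it can cost is 0.4% and 5%. Pooling, if it were done, would halve the expected contrast. These results assume equal variance in the two sessions and a rho that the documents do not supply. This is a free improvement rather than a flaw that invalidates the analysis.

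**What to change.** Add to C.2.7, under Behavioral paradigms:

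- The efficacy analysis of the body-language task uses the post-dose session, with the matching pre-dose score as covariate (ANCOVA of the post-dose score on Drug and the pre-dose score), fitted for reaction times and for valence ratings.
- The target is the Drug effect on the planned type × nature contrast: social threat minus social non-threat, minus the same difference for non-social stimuli.
- Drug terms averaged over both sessions are not efficacy tests. A Drug × Time version, if kept, is secondary.

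Confirm the stimulus categories when the score is defined. C.2.7 has a social/non-social factor, but C.2.2 mentions only threat and non-threat body language, so the two should be reconciled.

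The cost is a few sentences and one degree of freedom for the covariate. No new data are needed, because the pre-dose task is already in the visit schedule. The text should be fixed before unblinding.

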In the present project, 224 PSI subjects will be randomized to a single oral dose of PREG 400mg (n=112), or placebo (PBO, n=112), while behavioral responses and neuro-active steroid levels will be measured *before and after* study drug/placebo administration. This project is innovative is several ways. First, it is the first study of its kind to test the effect of PREG in individuals high in PSI. Second, it strategically combines multiple lines of investigation – behavioral, psychopharmacology, neuroimaging, and advanced statistical techniques (e.g. brain microstate identification via root mean square error modeling; bootstrapping) --- often carried out separately. More precisely, the proposed study aims to test a proof-of-concept that acute oral administration of PREG reduces PSI and its depressive symptomatology and improves attentional bias for social threats in a double-blind randomized research study combining a validated behavioral paradigm on social threat attention, intention understanding, and perception of others in male adults (aged 21-80) high in PSI. Validated self-report measures (e.g., depression, anxiety, objective social

isolation, life satisfaction) will also be used to examine change in symptom severity and subjective feelings. Third, it tests multiple layers of 'target engagement' including ALLO levels (determined by the state-of-the-art gas chromatography-mass spectrometry (GC-MS) quantification technology) in serum and saliva, and behaviors, and proximal and distal clinical outcomes. Importantly, the proposed study is the first to use PREG to engage the target ALLO to improve PSI. Such research has the potential to yield important insights into the neurobehavioral mechanisms of PREG on PSI and its underlying behavioral effects--- a first key step toward the development of adjunctive PREG therapy in individuals with PSI. Moreover, the proposed project is novel as it will attempt to establish PREG, a dietary supplement, as an agent intended to remediate the protracted reduction in the neurosteroid, ALLO, as a treatment for PSI in humans. The overarching objective is to use an acute, daily oral dose of PREG as an "ALLO normalizer" for six weeks to increase the likelihood patients with PSI will benefit from PREG. If successful, the novel use of PREG has the potential to reduce PSI and provide PSI patients with relief from PSI-related symptoms and disorders.

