Headaches are possible with high dosages or low dosages used over several days or weeks. Possible scalp hair loss if used daily for prolonged periods. Pregnenolone converts into DHEA, which in turn converts into testosterone and possibly on to DHT. It can also be converted into progesterone.

Irregularities of heart rhythm, Heart Palpitations, even on as low a dose as 5 mg. This can be serious in the elderly or those with heart rhythm disturbances.

Unknown effects on the thyroid gland or other organs and tissues.

Special Precautions & Warnings:

Pregnancy and breast-feeding: Although there is not enough known about the use of pregnenolone during pregnancy and breast-feeding, we'll avoid this risk by testing male participants only.

Hormone-sensitive condition such as breast cancer, uterine cancer, ovarian cancer, endometriosis, or uterine fibroids might have an interaction with pregnenolone: We'll exclude participants with any history of condition that might be made worse by exposure to estrogen.

8. Participants:

We will recruit 224 men (between 21 and 80) high in PSI and 12 Matched Healthy Controls (MHC) who are low in PSI.

9. Type and Number of Experimental Subjects:

We expect to collect data from a total of 36 subjects (between 21 and 80).

10. Potential Risks and Benefits:

The study will offer no direct benefits (besides monetary benefits and potential improvement of sexual desire) to participants. The questionnaires and behavioral task also present minimal risks, which may include boredom and fatigue from looking at pictures for a few minutes and anxiety or discomfort or distress related to responding to questionnaires.

11. CONTRAINDICATIONS:

• Estrogens interacts with PREGNENOLONE

Taking estrogen along with pregnenolone might cause too much estrogen to be in the body.

Some estrogen pills include conjugated equine estrogens (Premarin), ethinyl estradiol, estradiol, and others.

Progestin interacts with PREGNENOLONE

Progestins are a group of hormones. Taking other hormones along with progesterone pills might cause too much hormones in the body. This could increase the effects and side effects of hormone pills.

• Testosterone interacts with PREGNENOLONE

Taking pregnenolone along with a testosterone pill might cause too much testosterone in the body. This might increase the chance of testosterone side effects.

12. Monitoring of Safety:

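### The only power statement (36 subjects, three groups) does not describe the randomised comparison of 112 versus 112, and Section 9's total of 36 contradicts Section 8's 236

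*Combined protocol and SAP*

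**What the plan says.** **Power.** C.2.6 Power Analysis uses G*Power for a within-between interaction in a repeated-measures ANOVA. It states that "a total sample size of 36 for three groups will yield 95% power to detect a significant difference, with alpha = 0.05", for an effect size labelled Cohen's d of 0.35. It gives no outcome, SD, number of measurements or correlation between measurements.

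**Randomised design.** Section 3 (Innovation) and Section 7 (The Approach) both say that "224 PSI subjects will be randomized to a single oral dose of PREG 400mg (n=112), or placebo (PBO, n=112"; the dose-range rationale says the same. Section 7 adds an undosed comparison group: "A group of Matched Healthy Controls (MHC) who are low in PSI (n=12) and will not receive PREG".

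**Enrolment totals.** Section 8: "We will recruit 224 men (between 21 and 80) high in PSI and 12 Matched Healthy Controls (MHC) who are low in PSI". Section 9, immediately after: "We expect to collect data from a total of 36 subjects (between 21 and 80".

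**Analyses.** C.2.7 plans a Drug (PREG, PBO) x Time (before, after) ANOVA for the questionnaires. For the body-language task it plans a Drug x stimulus type x stimulus nature ANOVA. The drug factor has two levels in each. C.2.7 also plans a MANOVA for differences between the study groups, without listing the groups. Hypotheses 1A and 2B bring in the matched healthy controls.

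**The concern.** A power statement should refer to the comparison that the trial randomises. This one differs from it in total (36 against 224) and in number of groups (three against two), and the number it justifies reappears in Section 9 as the planned total. The number that the design sections use has no justification anywhere.

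As a result, the plan does not say what effect the 112 versus 112 comparison was sized to detect, and the protocol carries two enrolment totals that differ by a factor of 236/36 = 6.6. Because 0.35 is not tied to a scale, it cannot be carried over to the two-arm design either.

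**Working it through.** **1. Totals.** Section 8: 224 + 12 = 236. Section 9: 36. The third group in the power statement may be the 12 controls, since 36/3 = 12 and "Control subjects will perform the same tasks at the same time, except they will not take any pills". But 112 + 112 + 12 = 236, not 36, and the controls are in neither planned ANOVA.

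**2. Reproducing the 36.** For a within-between interaction with k groups, m measurements, effect size f and correlation rho:

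- lambda = f² x N x m / (1 - rho)
- df1 = (k - 1)(m - 1), df2 = (N - k)(m - 1)
- power from the noncentral F distribution at alpha 0.05

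From the power statement: k = 3, N = 36, alpha = 0.05. From Section 7: m = 2, because "behavioral responses and subjective feelings will be tested at two time points (once before and once after". Assumed: 0.35 is f, rho = 0.5, equal groups, sphericity where m is above 2.

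- N = 36: lambda = 0.1225 x 36 x 2 / 0.5 = 17.64, df 2 and 33, power 95.7%.
- N = 33: lambda = 16.17, df 2 and 30, power 93.8%.

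So 36 is the smallest total in equal groups that reaches 95%, and the plan's figure is reproduced.

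**3. How far that match depends on the assumptions.**

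- With m = 2, power at 36 is 87% for rho 0.3 and 99.8% for rho 0.7. The minimum N equals 36 only for rho from about 0.48 to 0.52 (39 at 0.47, 33 at 0.53).
- With rho = 0.5, the minimum N is 30 for three measurements and 24 for four. Blood and saliva are sampled three times, so m = 2 is not the only possible value.

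**4. What 112 per arm can detect.** With two arms and two time points, the Drug x Time test is the two-sample t test on change. With n = 112 per arm, df = 222, two-sided alpha 0.05, and delta in SDs of the change score, the noncentrality is delta x sqrt(112/2) = 7.483 x delta.

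- 80% power: delta = 0.376.
- 95% power: delta = 0.484.

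**5. What 0.35 would mean at 112 per arm.**

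- If it is 0.35 SD of the change score: noncentrality 7.483 x 0.35 = 2.62, power 74%.
- If it is f, with m = 2 and rho = 0.5: lambda = 0.1225 x 224 x 2 / 0.5 = 109.8, power above 99.9%. Since lambda = delta² x 56, this is delta = sqrt(109.8/56) = 1.40 SD of change, four times the first reading.

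**The case against.** **The 36 is only a leftover; 224 is plainly intended.** Much of this stands. Section 3, the dose-range rationale, Section 7 and Section 8 all give 224, three of them with the 112/112 split. A reader might infer that the planned enrolment cannot be known; that is too strong. But 36 stands in the two places where sample size is formally stated. If it is a leftover, 224 has no calculation behind it.

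**A three-group calculation has a place.** Hypothesis 1A involves PREG, placebo and healthy controls, and the MANOVA of study groups may include the controls. This explains the three groups, but not a total of 36 alongside arms of 112, and it does not power the randomised comparison.

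**The mislabelled effect size is speculation.** It is an inference, and working step 3 shows how narrow the match is. A reader might go further and infer that, with 0.35 taken as d, 36 subjects would have a specific low power. The documents do not support any such figure: the conversion from d to the interaction f depends on the SD and on which difference (level or change) d refers to, and neither is stated.

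**224 is ample, so no harm is done.** Whether it is ample depends on what 0.35 means. The opposite inference, that the trial is underpowered, is equally unsupported.

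**Conclusion.** Wrong as written. Two conflicts can be read directly from the text and need no assumption: the power statement covers 36 subjects in three groups while the randomised comparison is 112 versus 112, and Section 9's 36 contradicts Section 8's 236. That the 36 comes from another design is probable but inferred.

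The effect-size label is doubtful rather than proven wrong; that part rests on an assumed two measurements and rho of 0.5. The detectable differences at 112 per arm (0.38 and 0.48 SD of change) assume complete data and two-sided alpha 0.05.

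The defect is a mismatched and missing justification. It is not evidence that 224 is too small, and no arm size implied by splitting the 36 should be used to judge the trial, because no section states one.

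**What to change.** (a) Reconcile Section 9 with Sections 3, 7 and 8 and the dose-range rationale: 224 randomised plus 12 controls, 236 in total.

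(b) Replace the 36-subject, three-group statement with one for the two-arm Drug x Time test on an outcome that the sponsor names. For example: *With 112 per arm with complete data and two-sided alpha 0.05, power is 80% for a between-arm difference in change of 0.38 SD of the change score and 95% for 0.48 SD.* This reports what 224 can detect; it does not derive 224. If a calculation behind 224 exists, give it. If not, say so.

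(c) State whether 0.35 is f or d, which SD it refers to, the number of measurements and the correlation assumed. Quote no power at 0.35 until this is settled.

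(d) Say that the new statement does not cover the Drug x stimulus type x stimulus nature ANOVA or the comparisons with the 12 controls.

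Cost: protocol wording only, with no added enrolment. The stated power may look less favourable than 95%, and the text will show that 224 has no stated derivation unless the sponsor supplies one.
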